B.2. Treatment of chronic HCV. Sustained viral response (SVR), defined as the absence of detectable virus 24 weeks after completion of therapy, reflects elimination of HCV infection because >95% of patients with such responses remain persistently free of detectable virus up to 10 years later.^{15,16} Combination pegylated interferon (IFN) and ribavirin therapy also reduces progression of liver fibrosis,¹⁷⁻²² reduces portal hypertension,²³ prevents development of liver cancer,²⁴⁻²⁶ improves quality of life,²⁷⁻²⁹ and lengthens survival.³⁰⁻³² Treatment is complex, however, because treatment limiting side effects are extremely common.^{10-12, 33-35} These include flu-like syndromes,³⁶ cytopenias¹⁰⁻¹² which may require reduction or discontinuation of medications or the administration of growth factors,^{37,38} and neuropsychiatric side effects.³⁹⁻⁴⁵ Other common side effects are anorexia, nausea, skin rash, diarrhea, arthralgias, headaches, dizziness, and impaired thought.^{10,45} Support for side effect management is a crucial feature of HCV care.

B.3. Efficacy of new HCV regimens for genotype-1 infected patients. Treatment with IFN and ribavirin has been associated with SVR rates of 40-50% in treatment-naive patients with genotype 1. In the ADVANCE trial, patients who were treated with IFN, ribavirin, and telaprevir achieved an SVR of 75%, compared to 44% in the IFN and ribavirin arm.⁴⁶ Rates of SVR were higher in telaprevir-treated patients regardless of stage of liver disease, race, or ethnicity. However, there was a two-fold higher incidence of adverse effects, including rash, nausea, and anemia, with telaprevir-based regimens compared to IFN and ribavirin.⁴⁶⁻⁴⁸ When patients discontinue treatment prior to 20 weeks, the SVR rate is markedly decreased - only 23%.⁴⁷ Support for keeping patients on treatment is also crucial to maximize rates of SVR. The FDA has recently approved treatment of genotype-1 infected patients with 12 – 24 weeks of fixed-dose (ledipasvir and sofosbuvir), and this is associated with SVR rates of >95% (www.hcvguidelines.org).

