The above data demonstrate: (1) our ability to enroll and retain HCV-infected IDUs; (2) efficacy of enhanced mDOT v. standard mDOT; and (3) promising early outcomes with telaprevir-based therapy. However, because this pilot RCT was not powered to demonstrate increased SVR with mDOT (and both arms included some degree of DOT), we now propose a definitive study to determine if DOT is associated with increased SVR for genotype-1 patients, and whether DOT is cost-effective.¹²⁹ We will have sufficient power to answer this question as treatment for genotype-1 patients is more effective (SVR=75%),⁴⁶ we will include only genotype-1 patients, and all medications will be self-administered in the proposed TAU arm.

D.1.5. Concurrent Group Treatment (CGT). In 2009, we implemented a group treatment model of HCV care. To date, 39 patients have initiated CGT (including 34 enrolled in the mDOT study described above). Early treatment outcomes are promising, with 89% of patients completing at least 80% of planned treatment duration, and only 2 patients discontinuing treatment because of side effects. Of the first 20 patients who initiated CGT, 80% achieved an end of treatment response and 55% achieved SVR, including 57% of those

with genotype-1 (half active drug users).¹³⁰ Eight CGT patients have initiated telaprevir-based regimens, 7 of 8 had 4 week HCV VL <43 IU, 5 out of 8 had undetectable VL, with one discontinuing treatment. These data demonstrate that CGT is a promising model of care for treating IDUs. However, since patients were not randomized, it is possible that CGT patients were more motivated than others. The 2 x 2 figure demonstrates the effects of each intervention (mDOT and CGT), as well as of their interaction. When

subjects were treated individually with mDOT, or when the subjects were treated with CGT (without mDOT), adherence and virological outcomes were better than without either intervention. However, the additive effects of mDOT and CGT appear modest. For this reason, as well as to increase generalizability, in the proposed study we will evaluate 2 models of intensive care: mDOT (both IFN and oral medications) and CGT (IFN directly-administered and oral meds self-administered). Both models must be rigorously tested to determine whether intensive models of care are superior to standard on-site care for achieving SVR.

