
 Obtain oral consent for brief screening using Einstein Committee on Clinical Investigations (IRB) screening consent template Brief screen in private room in methadone clinic to determine eligibility Discuss study procedures, risks and benefits of study participation Obtain written consent for 1) clinical trial participation; 2) study staff to use protected health information from methadone clinic records; 3) study staff to disclose protected health information in event of psychiatric distress
Methadone clinic chart review:

 Laboratory test results: HCV Ab, HCV viral load, HIV (within 1 year), HCV genotype/subtype, IL28B, APRI and FibroSURE (biomarker tests for liver fibrosis) Methadone clinic attendance and dose
Second screening visit (medical eligibility determination by [name]):

 Review of HCV-related labs (as above) and fibroscan or liver biopsy (if available) Review of HCV Treatment Evaluation Flow Sheet to confirm no previous HCV treatment and planned on-site treatment regimen: fixed dose (sofosbuvir and ledipasvir) Participants who meet all eligibility criteria scheduled for a baseline visit Randomization (stratified, blocked) generated by centralized computer program

D.6. Participant tracking and retention. We have extensive experience following HCV- and HIV-infected drug users in studies. In our ongoing RCT of directly observed HCV treatment, 24 week follow-up was 92%.¹²⁹ In our completed RCT of directly observed HAART, 24-week follow-up was 86%.¹⁴² At enrollment and subsequent visits, we will record: 1) participants' address, phone number, and social security number; 2) contact information of family or friends; 3) contact information of participants' community-based organizations; 4) contact information of case managers; and 5) locations where participants "hang out".

D.7. Randomization. We will recruit 150 patients (100 on fixed-dose sofosbuvir and ledipasvir), with patients randomized to mDOT, CGT, or TAU in a 1:1:1 ratio (50 subjects in each group) in variable block sizes of 3-6 via central, computer-generated randomization. Two special randomization strategies (stratification and blocking) will be used to avert imbalances in prognostic factors, and to ensure comparison

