D.11. Analytic plan. First, the success of randomization will be checked by comparing the mDOT, CGT and TAU groups on key variables, such as age, gender, ethnicity, race, HCV viral load, HCV subtype (1a vs. 1b), BMI, psychiatric history, active drug use, and social support.⁴⁶ By design, IL28B and stage of liver disease will be represented equally in each arm. Continuous variables will be compared between arms using the ANOVA or Kruskal-Wallis test, and categorical variables will be compared using chi-square or Fisher's exact tests. Variables that are not equally distributed will be included in multivariate models. In primary analysis, we will use the intention-to-treat principle, which preserves the advantages of a randomized design.

D.12.1. Hypotheses for Aim 1. We hypothesize that in the intensive intervention arms, compared to the control arm, rates of adherence, treatment completion, and SVR will be significantly higher, and that rates of resistance will be lower. We further hypothesize that the proportion of subjects in the intensive models of care arms who achieve an SVR will be equivalent to that observed in large registration trials.

D.12.2. Analytic plan for Aim 1. Adherence to DAAs, ribavirin, and IFN will be determined using electronic monitors and self report, as described above. Initially, adherence will be calculated as a single outcome for each subject, evaluated at the end of the study. We will use Chi-square tests or Fisher's exact test to compare the proportion of subjects who achieve high adherence rate ($\geq 80\%$) complete treatment, achieve SVR, and develop resistance in the three arms (mDOT, CGT, and TAU). If the omnibus equality test of adherence across the 3 groups is rejected, we will conduct the following 2 specific post-hoc pairwise tests with a Bonferroni adjusted 2-sided alpha= 0.025: mDOT vs. control, and CGT vs. control. This strategy will be applied to multivariable logistic regressions if any potential confounding variables not equally distributed between the study arms at baseline are identified.

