Adherence. Based on our pilot data, if we conservatively assume that 80% of subjects in both mDOT and CGT arms will achieve $\geq 80\%$ adherence (v. 50% in the TAU arm), we will have $> 87\%$ power to find a statistically significant difference. With the application of mixed-effects logistic regression to the repeatedly measured binary adherence outcome, power will be greater than 87% no matter how large the within-subject outcome correlation or intraclass correlation (ICC).

In our previous DOT study, mean adherence in the mDOT group was 87% (SD=12%, n=21), and mean adherence in the TAU group was 77% (SD=20%, n=19) which translates into a standardized effect size or Cohen's $d = 0.6$. Based on this effect size, the power of the mixed effects linear model for the repeatedly measured continuous adherence outcome will be greater than 90%, even if anticipated ICC is as high as 0.5.

Treatment completion. Based on our pilot data, if we assume treatment completion rates of 85% in CGT, 60% in mDOT, and 50% in TAU, we will have $> 80\%$ power to detect this difference.

SVR. We anticipate that SVR rates in the mDOT and CGT arms will be 70%, and $\leq 40\%$ in the TAU arm.^{13,70,82} The statistical power will be $> 80\%$. These are conservative estimates of effect sizes, as actual effect sizes will likely be larger because regimens now contain telaprevir which is taken 3x daily. Effects size for fixed-dose (ledipasvir and sofosbuvir) is likely to be lower.

Resistance. We estimate that 16% of intervention arm subjects v. 30% of TAU subjects will develop resistance. We are underpowered to detect this difference, and consider this an exploratory analysis.

Effectiveness of intensive models of care. We will determine the proportion (and 95% CI) of subjects in each of the intensive intervention arms to achieve SVR, and compare to results from large registration trials.

D.14. Limitations. In addition to the considerations noted in Section D., our results may not be generalizable to HCV-infected drug users not enrolled in methadone clinics. However, we believe that the intensive models we are testing, if efficacious, can and should be adopted in diverse settings and populations.

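### SVR in the intensive arms is to be called equivalent to registration trials from one mixed-regimen CI per arm, with no named benchmark, margin or split by regimen

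*Combined protocol and SAP*

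**What the plan says.** All references are to the combined protocol and SAP.

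- **Hypothesis (D.12.1).** Besides the comparisons with the control arm, the plan hypothesizes that the proportion achieving SVR in the intensive arms "will be equivalent to that observed in large registration trials".
- **Analysis (D.13, paragraph on effectiveness of intensive models).** "We will determine the proportion (and 95% CI) of subjects in each of the intensive intervention arms to achieve SVR". The same sentence then sets these figures beside registration-trial results, without saying which ones. No trial, rate, margin, decision rule, sample size or regimen-specific analysis is attached to this hypothesis.
- **Benchmarks.** B.3 reports that telaprevir triple therapy "achieved an SVR of 75%, compared to 44% in the IFN and ribavirin arm", and D.1.4 uses the same 75% to justify the design. B.3 and D.9.6 give more than 95% for ledipasvir/sofosbuvir. The opening summary adds a general figure of over 90% for direct-acting agents.
- **Regimen mix.** D.7: "We will recruit 150 patients (100 on fixed-dose sofosbuvir and ledipasvir", allocated 1:1:1 with 50 per arm. D.2 describes other participants on 48-week regimens and names telaprevir as an example. The stratification factors in D.7 are IL28B genotype and cirrhosis; regimen is not one of them.

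**The concern.** Two faults combine. First, the arm-level proportion averages over regimens whose cited registration results differ by 20 points or more, so neither cited rate is the right comparator for it. Because no comparator is named, it could be chosen after the results are known. Second, the only tool offered is a CI, and a CI that contains a benchmark shows only that the data are compatible with it. In an arm of 50, or a stratum of about 33, that leaves room for a deficit that most readers would not call equivalence.

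At stake is a public statement that on-site care for this population does, or does not, match registration-trial cure rates. As planned, that statement could be driven by the regimen mix or by imprecision.

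**Working it through.** **1. The plan's own SVR figure.** D.13 states power above 80% for 70%, 70% and 40% with 40 completers per arm, based on the three-group omnibus test. With an assumed alpha of 0.05, the mean rate is 0.60 and the noncentrality is 40 × (0.10² + 0.10² + 0.20²) / (0.60 × 0.40) = 40 × 0.06 / 0.24 = 10. On 2 df this gives 81.5%, so the figure reproduces. It concerns differences between arms; nothing comparable is given for the equivalence hypothesis.

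**2. Inputs for the check.** From the documents: 50 per arm; 100 of 150 on ledipasvir/sofosbuvir; benchmarks of 75% and more than 95% (95% used here). Assumptions: 33 of 50 per arm on ledipasvir/sofosbuvir, the other 17 all on telaprevir, and an SVR result for all 50.

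**3. Expected SVR in an arm that exactly meets both benchmarks.** (33 × 0.95 + 17 × 0.75) / 50 = (31.35 + 12.75) / 50 = 88.2%. With 25 of 50 on ledipasvir/sofosbuvir it is (23.75 + 18.75) / 50 = 85%; with 45 of 50 it is (42.75 + 3.75) / 50 = 93%.

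**4. How that arm would read.** Exact (Clopper-Pearson) 95% CIs: 43/50 gives 73.3% to 94.2%, and 44/50 gives 75.7% to 95.5%. So 43 or fewer responders put the CI wholly below 95%, and 44 or more put it wholly above 75%. With X = Binomial(33, 0.95) + Binomial(17, 0.75):

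| Outcome | Against 95% | Against 75% | Probability |
|---|---|---|---|
| X ≤ 43 | below | compatible | about 37% |
| X ≥ 44 | compatible | above | about 63% |

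Every possible result for this arm therefore reads differently against the two benchmarks. The probability that the CI lies wholly below 95% is 55% with Wilson intervals and 22% with Wald intervals. If the benchmark above 95% is really 96% to 99% and the arm meets it, the exact CI lies wholly below it in 49% to 87% of trials.

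**5. The opposite error.** For an arm 15 points below both benchmarks (80% and 60%), the expected SVR is (33 × 0.80 + 17 × 0.60) / 50 = 36.6 / 50 = 73.2%. The exact CI covers 75% when 31 ≤ X ≤ 43, which happens in about 97% of trials.

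**6. Coverage is not equivalence.** In the ledipasvir/sofosbuvir stratum, 33 × 0.95 = 31.35, so take 31/33 = 93.9%, with an exact CI of 79.8% to 99.3%. The deficit left open is 95 − 79.8 = about 15 points. If the true rate were 85%, the CI would still cover 95% in about 44% of trials.

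**7. What a margin would buy.** The plan gives none, so these are assumed. The probability that the exact 95% CI lies wholly within benchmark ± margin, when the true rate equals the benchmark, is:

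| Comparison | 10 points | 15 points | 20 points |
|---|---|---|---|
| Pooled arm of 50 against 88.2% (simple binomial) | 14% | 77% | 94% |
| Ledipasvir/sofosbuvir, n = 33, against 95% | 18% | 50% | 92% |
| Telaprevir, n = 17, against 75% | 0% | 0% | 0% |

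**The case against.** The strongest reply is that this is a supplementary external comparison with no test, and that the between-arm comparisons in D.12.2 do not depend on it. That is right, and it keeps the point minor.

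Four stronger inferences are tempting, and the documents do not support them:

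- *An arm matching both benchmarks will look like a shortfall.* This holds only against the rate above 95%. The plan never chooses that comparator, and against 75% the same arm looks better. Even the typical result, 44/50, has a CI that contains 95%.
- *Pooling gives a wrong answer whatever the margin.* It does not, if the benchmark is weighted by the arm's regimen mix: step 7 shows usable power at margins of 15 to 20 points. Equivalence cannot be shown under the plan as written, but that is because it names no benchmark or margin.
- *Each arm contains 33 and 17.* The documents give only the overall 100 of 150. Regimen is not a stratification factor, and telaprevir is only an example of the other regimens. Table 1 also lists starting the fixed-dose regimen as an inclusion criterion, so it is not fully clear whether the other 50 enter this comparison. Pooling itself is inferred from the absence of any regimen-specific analysis.
- *The deficit left open in the ledipasvir/sofosbuvir stratum is only about 11 points.* That comes from 32/33, an observed rate of 97% with a lower limit of 84.2%. The count that fits 95% is 31/33.

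What remains after these limits is the unnamed comparator for a mixed figure and the word *equivalent*. If only ledipasvir/sofosbuvir participants were compared, the mixing problem would disappear, but the second fault would remain.

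**Conclusion.** The concern holds in limited form. D.12.1 makes an equivalence claim that the analysis in D.13 cannot support, and the arm-level figure has no single applicable benchmark among those cited. Under the assumed 33/17 split, one true state of affairs can be reported as below 95% or as above 75%, and a real deficit on both regimens can pass as agreement with 75%. The matching rate moves with the split but stays between the two benchmarks over 25 to 45 of 50.

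The plan's own planning rate for the intensive arms, 70% in D.13, is below both benchmarks and so sits awkwardly with the hypothesis under any mix. The calculations for arms of 50 also assume that every participant has an SVR result. The documents do not say how a missing one would count; if the planned 20% attrition were counted as failure, 88.2% would become 0.80 × 88.2 = 70.6%.

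The point is minor. It affects one secondary claim, not the randomized comparisons.

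**What to change.** - **D.13:** report SVR with an exact 95% CI by regimen within each intensive arm, and set each against a named benchmark for that regimen. Compare any pooled arm figure only with a benchmark weighted by that arm's actual regimen mix.
- **D.12.1:** replace the equivalence hypothesis with an estimation statement: for each regimen, give the benchmark minus the lower confidence limit, so that the reader sees which deficits are excluded and which remain possible.

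This takes a few sentences and no new data or participants. The price is a weaker claim and thinner strata. With about 17 telaprevir participants per arm, 13/17 gives an exact CI of 50% to 93%, so that stratum should be labelled descriptive.

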For the analysis of repeatedly measured adherence (using 6 post-baseline time points and adherence as a continuous measure), we will apply mixed effects linear model to test if the 3 groups are significantly different. This model accounts for within-subject longitudinal outcome correlation by taking the subject-level intercept as random. The model will include potential confounding variables. If the omnibus equality test is rejected, we will conduct the 2 post-hoc pairwise tests described above. Concerning potential clustering effects in the CGT arm, we used pilot data (5 groups) to examine whether clustering influenced adherence. Between cluster variation was not significant, as tested by application of a random effects repeated-measure ANOVA model. Clustering in the GCT arm will be minimal, and we will not adjust for it in statistical or power analysis.

We will also apply mixed effects logistic regression to test the significance of mDOT and CGT on repeatedly-measured undetectable HCV VL throughout the intervention period, adjusting for substance use. Changes in illicit drug use will be analyzed using urine toxicology data from each visit, counting the “person-month” as a unit of analysis, and analyzing the proportion of person-months that are positive for use of illicit drugs using a chi-square analysis.

As secondary analyses, we will examine if mDOT and CGT effects, v. TAU, will be mediated by IMB components. We will assess IMB model mediators of adherence at baseline, and during the intervention, and will analyze changes in those variables from the baseline to the intervention period. The indirect effects of IMB mediators will be tested by assessing changes in coefficients of the intervention effect (mDOT or CGT) with and without IMB component(s) in mixed effects models. Confidence intervals of the mediated effects will be calculated by bootstrapping, and mediation assumed if confidence intervals do not include zero.

D.12.3. Hypotheses for Aim 2. We hypothesize that only a minority (~20%) of IDUs will develop resistance, and that the relationship between adherence and resistance will be quadratic.

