We will use the model to assess the cost-effectiveness of the 3 interventions: TAU, mDOT, and CGT. Primary outcomes will be projected life-expectancy, quality-adjusted life-expectancy (QALYs), lifetime costs, and incremental cost-effectiveness ratios measured in \$/QALY. We will forecast health and cost outcomes of each intervention for a hypothetical cohort of HCV patients using baseline study data on fibrosis, age, sex, and alcohol use, and study outcome data for each intervention including SVR, resistance, and retention in care. We will explore the potential impact of resistance mutations by varying the efficacy of subsequent HCV retreatment for patients with resistance who choose to be retreated. Lifetime costs will include the costs of the intervention received as well as projected future costs of HCV care depending on treatment effectiveness. Incremental cost effectiveness ratios will be calculated for TAU compared to no treatment and for mDOT and CGI compared to the next most expensive intervention, with costs and QALYs discounted at 3% annually according to standard practice.¹⁷³ The resulting ratios will be compared to a threshold of \$100,000 per QALY.¹⁷⁴⁻¹⁷⁵ To explore uncertainties in our results, we will perform one and 2-way sensitivity analyses on key input variables (e.g. probability of SVR and intervention cost) and probabilistic sensitivity analyses (PSAs) using second order Monte Carlo simulation on multiple variables.¹⁷⁶ For PSAs we will perform 1,000 simulations of a cohort of 100,000 individuals. The result will be a distribution of 1,000 model-based outcomes with a median and interquartile range that reflects underlying uncertainty in critical model parameters.

D.13 Power considerations Assuming a conservative attrition rate of 20%, 50 subjects per arm will begin the study, but 40 subjects per arm will complete it. For power calculations for repeatedly measured continuous or binary adherence outcomes, we will use the expected number of observations per subject. The power analysis is conducted based on the omnibus testing of equality across the three groups. It follows that at least one of the post-hoc pair-wise tests is powered to be rejected by this study design.

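### Behind adherence's own three-group omnibus test, the Bonferroni 0.025 is valid but stricter than needed: at 40 per arm it costs 5.5 points of power per comparison and 9.7 for both

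*Combined protocol and SAP*

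**What the plan says.** D.12.2 (Analytic plan for Aim 1) compares the three arms on high adherence, completion, SVR and resistance by chi-square or Fisher's exact test. The pairwise step is conditional: "If the omnibus equality test of adherence across the 3 groups is rejected", the plan runs "2 specific post-hoc pairwise tests with a Bonferroni adjusted 2-sided alpha= 0.025: mDOT vs. control, and CGT vs. control". The same section repeats the rule for repeatedly measured continuous adherence: "If the omnibus equality test is rejected, we will conduct the 2 post-hoc pairwise tests described above". The alpha of the omnibus test is not printed, and for the binary outcomes the gate is written for adherence only.

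D.13 (Power considerations) is open about its basis: "The power analysis is conducted based on the omnibus testing of equality across the three groups". It then concludes: "It follows that at least one of the post-hoc pair-wise tests is powered to be rejected by this study design". Power for each comparison, or for both, is not given. D.2 nevertheless hypothesises that both intensive models will be superior to TAU.

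**The concern.** The omnibus gate and the Bonferroni split both guard against a false claim in either of two comparisons. With exactly three groups and two comparisons against a common control, the gate alone does this at the nominal level:

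- If mDOT = TAU and CGT = TAU, all three arms are equal. No pairwise claim is possible unless the omnibus test falsely rejects, which is limited to 5%.
- If only one of the two nulls is true, only one false claim is possible, and its own 0.05 test limits it.

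Halving the pairwise alpha therefore buys no nominal familywise control within that endpoint, and it lowers the chance of showing that a given model, or both, beats TAU. The argument needs the endpoint's own omnibus test. It does not carry over to SVR or completion if their pairs sit behind the adherence gate.

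**Working it through.** **Inputs.** Binary adherence 80% mDOT, 80% CGT, 50% TAU (D.13). 50 randomised and 40 completing per arm (D.7, D.13). Pairwise alpha 0.025 (D.12.2). Assumed, because not printed: omnibus alpha 0.05.

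**1. The plan's own figure.** The omnibus noncentrality is λ = n Σ(pᵢ − p̄)² / [p̄(1 − p̄)] with p̄ = 0.70, so λ = 40 × (0.01 + 0.01 + 0.04)/0.21 = 11.43. On 2 df at 0.05 the power is 86.6% (86.3% by exact enumeration). D.13 prints more than 87%, so the figure is reproduced to within a point.

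**2. Power after the gate.** For every one of the 41³ possible outcomes, compute the 3 × 2 Pearson chi-square (critical value 5.99). For each pair compute 2n(a − b)²/[s(2n − s)], where a and b are the two counts and s = a + b (critical value 5.02 at 0.025, 3.84 at 0.05). Then sum the binomial probabilities of the outcomes in which the omnibus test and the pair(s) reject.

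| Binary adherence, pairwise 0.025 v 0.05 | Each | Both | At least one |
|---|---|---|---|
| 40 per arm, chi-square | 73.2 v 78.8% | 61.5 v 71.2% | 85.0 v 86.3% |
| 40 per arm, Fisher pairs | 65.9 v 73.9% | 51.6 v 62.3% | 80.2 v 85.4% |
| 50 per arm, same rates | 83.3 v 87.7% | 74.3 v 82.4% | 92.3 v 93.0% |
| 50 per arm, the 20% dropouts counted as failures (64/64/40%, assumption) | 53.9 v 62.8% | 38.3 v 54.5% | 69.5 v 71.1% |

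The 50-per-arm rows are shown because D.11 states "In primary analysis, we will use the intention-to-treat principle".

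In the first row the loss is 78.76 − 73.24 = 5.5 points per comparison and 71.18 − 61.48 = 9.7 for both. With the omnibus test held at 0.025 the loss would be 3.8 and 7.7 points; at 0.01, 2.5 and 4.9.

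**3. Continuous adherence.** Take d = 0.6 (D.13's mDOT figure, assumed for CGT too), ICC 0.5 and 6 time points. The effective d on subject means is 0.6/√[(1 + 5 × 0.5)/6] = 0.786. Power per comparison is 88.7% v 92.2% by simulation, adequate either way.

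**4. Error, 40 per arm, chi-square.**

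- All arms equal, own gate, pairs at 0.05: 4.3% (true rate 40%) and 4.7% (50%).
- All arms equal, no own gate, pairs at 0.05: 9.4% and 10.2%. At 0.025: 5.2% and 4.7%. This is the SVR case once an adherence gate has already passed.
- One true null, maximum over a grid of rates: 5.9% at 0.05 v 2.8% at 0.025 (50 per arm: 5.7% v 2.6%). Fisher pairs at 0.05: 3.3% (50 per arm: 3.5%).

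**5. SVR, only if it has its own gate.** At D.13's 70/70/40%: each 68.0 v 75.0%, both 54.6 v 67.9%, at least one 81.4 v 82.1%. These are not the powers for the current regimen, since D.13 adds: "Effects size for fixed-dose (ledipasvir and sofosbuvir) is likely to be lower". With 95% assumed in both intensive arms and 85%, 80% or 75% in TAU, power per comparison is 19 v 27%, 40 v 50% and 63 v 72%.

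**The case against.** The strongest reply is that nothing is broken. D.13 claims only that at least one comparison is powered, and that figure moves by 1.4 points. A conservative alpha is a legitimate choice, the more so as Aim 1 has four outcomes and no control across them. All of that is true, and it is why the point is optional. But D.2 hypothesises that both models beat TAU, so power for each and for both bears on the trial's own question.

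Second, the gain depends on the test. If actual error must stay below 5%, the safe version is Fisher pairs at 0.05 (73.9% each, 62.3% both). That is only 0.6 and 0.8 points above chi-square at 0.025, which the plan already allows. This stands. Like for like the gain remains: 5.5 and 9.7 points for chi-square, 7.9 and 10.7 for Fisher.

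Third, the slack does some work here. On the CGT arm the plan says: "Clustering in the GCT arm will be minimal, and we will not adjust for it in statistical or power analysis". With five groups of eight and an assumed ICC of 0.05, simulated CGT v TAU error is 7.8% at 0.05 against 4.0% at 0.025; at ICC 0.02 it is 6.5% against 3.1%. This is a real cost, small only if clustering is as minimal as the plan expects.

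Fourth, the 80/80/50 rates come from pilot data on interferon and ribavirin, while D.9.6 puts all new subjects on ledipasvir/sofosbuvir. If adherence were 90/90/80% (assumed), power per comparison would be 13.6% v 17.5%, inadequate under either rule.

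**Conclusion.** The concern holds as an efficiency point. For adherence, which has its own omnibus gate, 0.025 per pair is valid but stricter than nominal 5% familywise control requires. At D.13's rates, 40 per arm, chi-square tests and an assumed omnibus alpha of 0.05, it costs 5.5 points of power per comparison and 9.7 for both. With 50 per arm at the same rates it costs 4.4 and 8.2. D.13's claim about at least one comparison roughly stands under either rule. The conclusion does not extend to endpoints without their own omnibus test, gives no control across endpoints, and rests on adherence rates that may not describe the current regimen.

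**What to change.** In D.12.2, for each endpoint that will have pairwise tests, run that endpoint's own three-group omnibus test at a stated alpha of 0.05. Only if it rejects, test mDOT v TAU and CGT v TAU each at two-sided 0.05, and describe this as a closed procedure. Keep 0.025 for any endpoint whose pairs are not gated by its own omnibus test. Name Fisher's exact test for the pairs if actual error must stay below 5%. In D.13, replace the sentence inferring pairwise power from omnibus power with a short table of power for each comparison, at least one, and both.

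The cost is a few sentences and a small table, with no extra patients. The price in error control is the lost slack: up to 5.9% with chi-square pairs at 40 per arm, and less protection against unadjusted CGT clustering. If the team thinks that clustering may be material, this is a reason to keep 0.025 for CGT v TAU or to adjust for the groups. The change does not bring each comparison to 80% power at 40 per arm.

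### The continuous-adherence mixed model makes no provision for unequal variances, so if the pilot SDs (12% and 20%) carry over, the pairwise comparisons with TAU can run off their 0.025 level.

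*Combined protocol and SAP*

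**What the plan says.** D.12.2 analyses adherence in two ways. The first compares the proportion of subjects with at least 80% adherence by chi-square or Fisher's exact test. The second, at issue here, is a mixed effects linear model for the repeated measurements, "using 6 post-baseline time points and adherence as a continuous measure". On variance it says only: "This model accounts for within-subject longitudinal outcome correlation by taking the subject-level intercept as random". Potential confounders are added as covariates. No residual structure, arm-specific variance or robust standard error is named there or elsewhere.

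On testing, D.12.2 says: "If the omnibus equality test is rejected, we will conduct the 2 post-hoc pairwise tests described above". Those two tests are set out earlier in the section as "Bonferroni adjusted 2-sided alpha= 0.025: mDOT vs. control, and CGT vs. control".

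D.13 gives the pilot figures: "mean adherence in the mDOT group was 87% (SD=12%, n=21), and mean adherence in the TAU group was 77% (SD=20%, n=19". It condenses them into a standardized effect of 0.6 and states that power "will be greater than 90%, even if anticipated ICC is as high as 0.5". No SD is given for CGT.

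**The concern.** A random-intercept model, fitted in the usual way, has one between-subject variance and one residual variance for all three arms. The plan's own pilot suggests the arms differ: the variance ratio is 400/144 = 2.78. Unequal spread is also plausible in principle, because adherence is bounded at 100% and the intensive arms aim to push it towards that bound.

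With two equal arms this would not matter, because the pooled and unpooled standard errors coincide. With three arms, each comparison with TAU borrows variance from an arm outside the comparison. The pairwise p-values may then not run at 0.025, and the matching 97.5% intervals may not have their stated coverage. These two comparisons answer Aim 1's question of whether either intensive model beats standard on-site care.

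**Working it through.** **Inputs.** From D.13: SDs of 12% (mDOT, n=21) and 20% (TAU, n=19), ICC up to 0.5, 50 per arm starting and 40 completing. From D.7: 1:1:1 allocation. From D.12.2: six time points, and two-sided pairwise alpha of 0.025 after an omnibus test. Assumed: a CGT SD of 12% to 20%, and an omnibus level of 0.05 (the plan states none).

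**Reproducing the plan's figures.** The difference is 87 − 77 = 10 points. The df-weighted pooled SD is 16.29, so d = 0.61; the root-mean-square SD is 16.49, also d = 0.61. The stated 0.6 is confirmed. The variance of a subject mean is SD² × (1 + 5 × 0.5)/6 = 0.583 × SD². With both intensive arms at d = 0.6 and TAU at 0, the omnibus noncentrality is 40 × 0.24/0.583 = 16.5 and power is 95.7%. The claim of more than 90% therefore holds in that case. It is 88.4% if CGT lies midway between mDOT and TAU.

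**Effect of a common variance.**

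- Model SE = √(2 × mean of the three variances / 40)
- Correct SE = √((SD² of the intensive arm + 400)/40)
- Actual level ≈ 2 × (1 − Φ(2.241 × model SE / correct SE))

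SEs are in adherence points before the repeated-measures factor. If the ICC is the same in every arm, that factor cancels from the ratios.

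| CGT SD | Mean variance | Model SE | mDOT v TAU: correct SE, ratio, level | CGT v TAU: correct SE, ratio, level |
|---|---|---|---|---|
| 12% | (144+144+400)/3 = 229.3 | 3.39 | 3.69, 0.918, 0.040 | 3.69, 0.918, 0.040 |
| 16.5% | (144+272+400)/3 = 272 | 3.69 | 3.69, 1.00, 0.025 | 4.10, 0.900, 0.044 |
| 20% | (144+400+400)/3 = 314.7 | 3.97 | 3.69, 1.076, 0.016 | 4.47, 0.887, 0.047 |

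The mDOT v TAU standard error is exact when the CGT variance equals (144 + 400)/2 = 272, that is, an SD of 16.5%. No CGT SD in the range makes both tests exact. Coverage of the 97.5% interval for CGT v TAU is 1 − 0.040 = 96.0% at best and 1 − 0.047 = 95.3% at worst.

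**Checks.** Simulating 200,000 trials per case gave the same levels to within simulation error. Tests with arm-specific variances ran at 0.025–0.026 throughout. Fitted random-intercept models (60 per case, six visits, ICC 0.5) behaved as predicted. With SDs 12/12/20 (mDOT/CGT/TAU), the mean model SE was 2.56 against a correct 2.82. With SDs 12/20/20 it was 3.00, against 2.82 for mDOT v TAU and 3.42 for CGT v TAU.

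**With the omnibus gate.** When all arm means are equal, the omnibus test rejects in 5.3–5.5% of trials, and the chance of any false pairwise claim is 4.5–5.2% (5.7–6.5% without the gate). If mDOT gains the pilot 10 points and CGT gains nothing, the gate opens in 96–99% of trials. CGT is then falsely declared different from TAU at about 0.040–0.047.

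**The case against.** A reader might infer that the standard errors against TAU are wrong outright. The documents do not support that, for three reasons. First, the sentence in D.12.2 explains how within-subject correlation is handled. It does not assert equal variances or rule out robust standard errors, so a common variance is the usual default and not a stated commitment. Second, the CGT SD is not given, and at about 16.5% the mDOT v TAU standard error is exactly right. Third, the SDs come from 21 and 19 subjects: the variance ratio of 2.78 has a normal-theory 95% interval of about 1.1 to 7.1.

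The setting has also changed. The pilot in D.1.4 used interferon and ribavirin with pill counts. New enrolment uses a once-daily fixed-dose regimen with electronic monitoring, and D.9.4 adopts blister packs to raise control-arm adherence. Higher TAU adherence could narrow the TAU spread and the ratio. All of this stands, and it makes the point conditional.

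A reader might also take the ungated levels as the plan's overall error rate. They are not: with all arms equal, the gate keeps any false pairwise claim near 5%. That reassurance ends once one arm works, because the gate is then almost always open for the other, and it never applied to confidence intervals.

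The reach is limited too. The chi-square or Fisher comparison of the proportion with at least 80% adherence is untouched, and the omnibus test is nearly so.

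**Conclusion.** The point holds conditionally. The plan names only a random intercept and makes no provision for unequal variances, while its own pilot SDs differ. If they carry over with 40 per arm, the CGT v TAU standard error is too small by 8–11% at every CGT SD from 12% to 20%, and its 0.025 test runs at up to nearly twice that level. For mDOT v TAU, both the size and the direction of the error depend on the unknown CGT SD. The result assumes equal numbers at analysis; unequal dropout could change it. This is a moderate weakness in one of the two adherence analyses, worth correcting because the remedy is cheap and holds the level whatever the CGT SD proves to be.

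**What to change.** Add to D.12.2 that the continuous-adherence model will be fitted with arm-specific between-subject and residual variances, using Satterthwaite or Kenward-Roger degrees of freedom. Alternatively, specify subject-level sandwich standard errors with a small-sample correction. Apply the choice to the omnibus test, both pairwise tests and their intervals.

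The cost is one sentence, one model option and a few extra variance parameters. For a 10-point gain with ICC 0.5 and six visits, simulated mDOT v TAU power falls from about 93% to 89% if the CGT SD is 12%, and rises from about 86% to 89% if it is 20%. By normal approximation, CGT v TAU power for the same gain falls from about 83% to 75% if the CGT SD is 20%. Where power falls, the excess came from a test running above its stated level.
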